## 14.8. Appendix 8: Values of Potential Clinical Importance

To identify laboratory values of potential clinical importance, National Cancer Institute Common Terminology Criteria for Adverse Events (NCI-CTCAE v5.0) will be used to assign grades for laboratory parameters including clinical chemistry, hematology, liver function tests, QTc (Fridericia's) values, and vital signs (heart rate, blood pressure, temperature).

Reference ranges for all laboratory parameters collected throughout the study are provided by the laboratory. A laboratory value that is outside the reference range is considered either high abnormal (value above the upper limit of the reference range) or low abnormal (value below the lower limit of the reference range). Note: a high abnormal or low abnormal laboratory value is not necessarily of clinical concern. The laboratory reference ranges will be provided on the listings of laboratory data. Clinical laboratory test results outside of the reference range will be flagged in the listings.

### 14.8.1. ECG

The following criteria will be used to flag electrocardiogram (ECG) values that are values of potential clinical importance:

To identify QTc (Fridericia's) values of potential clinical importance, NCI-CTCAE v5.0 will be used to assign grades (see adverse event 'Electrocardiogram QT corrected interval prolonged'). The CRF collects QTcF. Note that there is a slight inconsistency between CTCAE v5.0 and ICH E14 (Absolute QTc interval prolongation). It was decided to align with CTCAE for the oncology standard categories.

| ECG Parameter               | Potential Clinical Importance (PCI) Range                          | Unit |
|-----------------------------|--|------|
| Absolute QTcF interval      | ≥450 to <481 (Grade 1)
≥481 to <501 (Grade 2)
≥501 (Grade 3) | Msec |
| Increase from baseline QTcF | Increase of ≥31 to ≤60
Increase of >60                          | Msec |

The following criteria will be used to flag other ECG values that are values of potential clinical importance:

| ECG Parameter         | Potential Clinical Importance (PCI) Range | Unit |
|-----------------------|---|------|
| Absolute PR interval  | <110 (Low)
>220 (High)                 | Msec |
| Absolute QRS interval | <75 (L)
>110 (H)                       | Msec |

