Nausea	
 • Grade 3 persisting >3 days despite BSC^a
Vomiting	
 • Grade 3 or 4 persisting > 3 days despite BSC^a
Diarrhea	
 • Grade 3 or 4 persisting > 3 days despite BSC^a
Fatigue	
 • Grade 3 persisting > 5 days
Hypertension	
 • Grade 3 that cannot be controlled with medical therapy • Grade 4
ECG-change	
 • > 20 msec extension of the QRS-interval compared to baseline
Laboratory abnormality	
 • Grade 3 persisting > 3 days despite BSC^a • Grade 4
Any other	
 • Grade 2 leading to frequent dose interruptions despite BSC^a and limiting GSK3368715 dosing to <80% of expected dose • Grade 2 requiring delay of GSK3368715 administration for > 14 days • Grade \geq3

DLT criteria for Hematologic Toxicity	
Neutropenia	
 Grade 3 persisting > 3 days despite BSC^a Febrile neutropenia Grade 4
Thrombocytopenia	
 Grade 3 persisting > 3 days despite BSC^a Grade 3 associated with clinically significant hemorrhage Grade 4
Any other ^b	
 Grade 2 and 3 leading to frequent dose interruptions despite BSC^a and limiting GSK3368715 dosing to < 80% of expected dose Grade 3 persisting > 3 days despite BSC^a Grade 4
Venous Thromboembolism	
 Grade 2 venous thromboembolism (VTE) that requires systemic anticoagulation or VTE Grade ≥ 3 during the first 8 (± 1) weeks or until study discontinuation (e.g., disease progression), whichever occurs sooner.

ALT=alanine aminotransferase; AST=aspartate aminotransferase; BSC=best supportive care; DLT=dose-limiting toxicity; ECG=electrocardiogram; ULN=upper limit of normal

- a. Best supportive care if available, according to institutional standards
b. With the exception of lymphocytopenia

For participants who experience a toxicity that meets the criteria of DLT, administration of GSK3368715 will be held pending management and resolution of the toxicity.

Participants who withdraw from the study before completing 21 days of intervention for reasons other than DLT may be replaced at the discretion of the sponsor.

Guidance for the management of toxicity, including dose modification algorithms, is provided in [Appendix 12](#).

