 - b) Any history of coronary artery disease, including acute coronary syndromes, myocardial infarction, unstable angina, and history of coronary angioplasty, or stenting
 - c) Presence of a cardiac pacemaker or implanted defibrillator.
 - d) AV-block (asymptomatic 2nd degree Type II or 3rd degree and any degree AV block if related to heart disease or if symptomatic), RBBB (right bundle branch block), LBBB (left bundle branch block), and any fascicular hemiblocks.
 - e) A QRS interval at Screening or Baseline ≥ 110 msec.
 - f) Patients with any symptomatic or sustained arrhythmias (past or present), including but not limited to:
 - Atrial fibrillation.
 - Atrial flutter
 - Ventricular tachycardia
 - Ventricular fibrillation
 - Supraventricular tachycardia
 - g) Current or past congestive heart failure.
 - h) Evidence of a left ventricular ejection fraction below the institutional lower limit of normal on Screening echocardiogram.
 - i) Evidence of significant structural heart disease on echocardiography at Screening (including any valvular disease greater than “mild” in severity)
 - j) Cardiac troponin > upper limit of the reference range at Screening.

Prior or Concomitant Anti-cancer Therapies

9. Treatment with any local or systemic anti-neoplastic therapy or investigational anti-cancer agent within 14 days or 4 half-lives, whichever is longer, up to a maximum wash-out period of 28 days prior to initiation of study drug administration

EXCEPTION NOTE: Anti-androgen therapies for prostate cancer, such as bicalutamide, must be stopped 28 days prior to first dose of GSK3368715. Second-line hormone therapies such as enzalutamide or abiraterone should be stopped 14 days prior to enrolment. Participants with prostate cancer may remain on (i) luteinizing hormone-releasing hormone (LHRH) agonists or antagonists and/or (ii) low-dose prednisone or prednisolone (up to 10 mg/day).

Nitrosureas and mitomycin C must be stopped within 42 days prior to first dose of GSK3368715.

10. Allogeneic hematopoietic stem-cell transplantation
11. Toxicities from previous anti-cancer therapies have not resolved to baseline or NCI-Common terminology criteria for adverse events (CTCAE) v5 \leq Grade 1 (except fatigue and alopecia [permissible at any grade] and peripheral neuropathy [which must be \leq Grade 2]) at the time of starting study intervention.

Prior or Concomitant Therapies:

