7.1.3. QRS Interval Stopping Criterion

An increase in the QRS interval of > 20 ms from baseline.

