10.12.1. Management of Selected Toxicities

Table 14 Dose Adjustment/Stopping Safety Criteria

Toxicity	Dose Adjustment/ Stopping Criteria	Management Guidelines
Thrombocytopenia	Grade 1 & 2	Continue dosing at same dose level with weekly or more frequent monitoring as necessary
	Grade 3	
 Hold GSK3368715 until resolved to Grade ≤ 1 within ≤ 14 days Monitor complete blood count (CBC) at least twice a week Discuss with GSK Medical Monitor Re-start GSK3368715 at a reduced dose Discontinue GSK3368715 if not resolved to Grade ≤ 1 within ≤ 14 days
	Grade 4	
 Discontinue GSK3368715 Monitor CBC every 2-3 days.
Anemia	Grades 1 & 2	Continue dosing at same dose level with weekly or more frequent monitoring as necessary
	Grade 3	
 Hold GSK3368715 until resolved to Grade ≤ 1 within ≤ 14 days. Transfuse and treat as necessary. Monitor CBC at least twice a week. Discuss with GSK Medical Monitor. Re-start GSK3368715 at a reduced dose. Discontinue GSK3368715 if not resolved to Grade ≤ 1 within ≤ 14 days.
	Grade 4	
 Discontinue GSK3368715. Transfuse and treat as necessary. Monitor CBC every 2-3 days.
PR Interval	An increase in the PR Interval to >250 msec	
 This interval should be based on the average of the triplicate ECGs Discontinue GSK3368715 Contact the medical monitor Maintain proper electrolytes similar to recommendations for QTcF

Toxicity	Dose Adjustment/ Stopping Criteria	Management Guidelines
QRS Interval	An increase of >20% from baseline	
 This interval should be based on the average of the triplicate ECGs Discontinue GSK3368715 Contact the medical monitor Maintain proper electrolytes similar to recommendations for QTcF
QTcF	If >30msec and < 60 msec change from baseline AND manual QTcF <500 msec (average of three ECGs over at least 15 minutes)	
 Continue current dose of GSK3368715 
 Supplement electrolytes, particularly potassium and magnesium, to recommended levels: 
 Maintain serum potassium > 4 mol/L Maintain serum magnesium levels >0.85 mmol/L Discontinue any concomitant medications with potential for QTcF prolongation. Consider 24 hour or longer telemetry monitoring if clinically indicated.

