**CONFIDENTIAL**

207675

| ICH: Listings      |                   |                             |   |                          |                    |
|---------------------------|-------------------|-----------------------------|---|--------------------------|--------------------|
| No.                | Population | IDSL / Example Shell | Title  | Programming Notes | Deliverable |
| Deaths             |                   |                             |   |                          |                    |
| 23.                       | All Treated       | DTH3                        | Listing of Deaths   | ICH E3                   | SAC                |
| All Laboratory     |                   |                             |   |                          |                    |
| 24.                       | All Treated       | LB5A                        | Listing of All Chemistry Laboratory Data for Participants with Any Value of Outside Normal Range  | ICH E3                   | SAC                |
| 25.                       | All Treated       | LB5A                        | Listing of All Hematology Laboratory Data for Participants with Any Value of Outside Normal Range | ICH E3                   | SAC                |
| 26.                       | All Treated       | LB14                        | Listing of Laboratory Data with Character Results   | ICH E3                   | SAC                |
| ECG                |                   |                             |   |                          |                    |
| 27.                       | All Treated       | EG3                         | Listing of All ECG Values for Participants with Any Value of Potential Clinical Importance        | IDSL                     | SAC                |
| 28.                       | All Treated       | OECG5A                      | Listing of QTcF Values of Potential Clinical Importance   |                          | SAC                |
| Vital Signs        |                   |                             |   |                          |                    |
| 29.                       | All Treated       | OVT7A                       | Listing of Vital Signs with Values of Potential Clinical Importance                               |                          | SAC                |

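### The SAP flags QRS only by absolute value, so a rise from baseline that meets the protocol's QRS criterion can be left out of the participant-level ECG listing

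*SAP*

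**What the plan says.** SAP Section 14.8.1 sets the limits for flagging ECG values of potential clinical importance.

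- QTcF has two rows: absolute bands starting at 450 ms, and "Increase from baseline QTcF", with bands of 31 to 60 ms and above 60 ms.
- PR has one absolute row: below 110 or above 220 ms.
- QRS has one absolute row, "Absolute QRS interval": below 75 ms is Low and above 110 ms is High.

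The participant-level ECG displays are in SAP 14.10.8. Listing 27 is titled "Listing of All ECG Values for Participants with Any Value of Potential Clinical Importance"; Listing 28 covers QTcF only. The ECG tables in SAP 14.10.5 are 3.16 (findings) and 3.17 (change from baseline by visit).

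The protocol treats QRS as a change from baseline in three places.

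- Table 6 (Section 4.1.3) lists "> 20 msec extension of the QRS-interval compared to baseline" among the DLT criteria.
- Section 7.1.3 sets the stopping criterion: "An increase in the QRS interval of > 20 ms from baseline".
- Table 14 (Section 10.12.1) gives the QRS criterion as "An increase of >20% from baseline".

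Exclusion criterion 8(e) in Section 5.2 rules out "A QRS interval at Screening or Baseline ≥ 110 msec". Section 9.6.2.4 says ECG data will be summarised against criteria fixed in advance and leaves the detail to the RAP.

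**The concern.** An absolute limit and a change limit select different people. Listing 27 is the planned display that would show, from the recorded ECGs, which participants had a QRS value of concern, and its selection contains no change-from-baseline rule for QRS. A participant can meet the protocol's own criterion and stay inside the absolute limits, while another is listed for a trivial change near the upper limit.

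QRS is a named risk. Protocol Section 2.2.1.1 reports dose-dependent PR and QRS increases in rats and dogs and suggests a sodium-channel effect as a possible cause, and Section 2.3.1 carries this into the risk table. SAP Section 1 records that Amendment 3, the version it is written to, changed the DLT and stopping criteria for QRS. At stake is whether the final report can show, independently of what investigators reported, how many participants at each dose met the QRS criterion.

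**Working it through.** The plan gives no figure of its own on this point, so the check compares thresholds.

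**Inputs**

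- SAP 14.8.1: QRS is flagged if below 75 or above 110 ms.
- Protocol Table 6 and Section 7.1.3: criterion met if post − baseline > 20 ms.
- Protocol Table 14: criterion met if post > 1.2 × baseline.
- Protocol Section 5.2: eligible baseline b < 110 ms.

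**Step 1, the 20 ms wording.** A rise is unflagged on QRS if b ≥ 75, post > b + 20 and post ≤ 110. Such a value exists only if b + 20 < 110, that is b < 90. The affected baselines are therefore 75 ≤ b < 90, or 15 whole-number values (75 to 89). The unflagged range has width 110 − (b + 20) = 90 − b: 15 ms at b = 75, shrinking to 1 ms at b = 89. For 90 ≤ b < 110, any rise above 20 ms passes 110 and is always flagged.

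**Step 2, the 20% wording.** An unflagged value exists if 1.2b < 110, that is b < 110/1.2 = 91.7 ms. The gap exists under either wording.

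| Baseline (ms) | 20 ms rule met above | Unflagged | 20% rule met above | Unflagged |
|---|---|---|---|---|
| 75 | 95 | >95 to 110 | 90 | >90 to 110 |
| 85 | 105 | >105 to 110 | 102 | >102 to 110 |
| 89 | 109 | >109 to 110 | 106.8 | >106.8 to 110 |
| 90 | 110 | none | 108 | >108 to 110 |
| 95 | 115 | none | 114 | none |
| 100 | 120 | none | 120 | none |

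The two wordings coincide only where 0.2b = 20, at b = 100 ms.

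**Step 3, the opposite error.** 108 + 3 = 111 ms is flagged High although the change is 3 ms.

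**Step 4, the other intervals.** Protocol 7.1.2 stops on QTcF above 500 ms or a change above 60 ms. The SAP bands start at 450 ms and include a row for increases above 60 ms, so both are covered. Protocol 7.1.4 stops on PR above 250 ms, inside the SAP flag at 220 ms. Only QRS can meet its stopping criterion with no flag on that interval.

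**Step 5, other displays.**

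- Table 3.17: SAP 5.2 includes the maximum by default and 8.5.2 does not override it, so the largest change per visit and dose level should appear. It does not show who or how many, and SAP 5.4 and 14.5.2 keep unscheduled ECGs out of such summaries.
- Table 3.16 counts normal and abnormal readings, with no interval threshold.
- Table 3.22 and Listing 22 (DLTs), Listing 14 (adverse events), Table 3.7 and Listing 19 (events leading to discontinuation) and Listing 3 (reasons for discontinuation) would carry a QRS event if the investigator reported it as such.

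**The case against.** The strongest case against is that little would be lost. A QRS event judged to be a DLT has its own table and listing; a clinically significant ECG worsening is an adverse event under protocol Appendix 3; and a discontinuation is listed with its reason. Table 3.17 should show the maximum change, so an exceedance at a scheduled visit would not be hidden. Listing 27 prints every ECG value for anyone with any flag, so a PR or QTcF flag would bring in the QRS data too. Protocol Section 2.2.1.4.3 reports a concentration–QRS slope near zero over more than 400 points in 19 participants. Enrolment has ended, and Listing 27 is a final display that drives no dose decision.

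Most of this stands and limits the point. A reader might infer that the planned displays would show no trace of QRS concern in a participant with a DLT. The documents do not support that, because the DLT and adverse event displays are a separate route. Nor is a rise above 20 ms by itself a DLT: for an event of this kind Section 4.1.3 also requires investigator-judged clinical relevance and attribution within the first 21 days. A reader might also infer a departure from protocol Section 9.6.2.4, but that section leaves the criteria to the RAP and does not require them to reproduce the stopping rules.

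What the objection does not remove is that these other routes depend on investigator reporting, that a maximum identifies no one, and that a flat average slope says nothing about individual exceedances.

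**Conclusion.** The point holds as a gap in the ECG-based, participant-level display. With a baseline QRS from 75 to below 90 ms (below about 91.7 ms under the percentage wording), a participant can meet the protocol's QRS change criterion at or below 110 ms and be left out of Listing 27 unless another ECG value is flagged. It would be wrong to read this as covering every low baseline, since a value below 75 ms is flagged Low, or every participant, since baselines of 92 ms and above are always caught under both wordings.

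The number affected cannot be calculated: the documents give no baseline QRS distribution, and it may be none.

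The conclusion assumes that Listing 27 is selected on the SAP 14.8.1 limits and that the Low limit applies to baseline as well as later values. If selection used post-baseline values only, some baselines below 75 ms would join the gap. The claim about Table 3.17 assumes that its shell follows the SAP 5.2 default. The matter affects the completeness of safety reporting, not the dose decisions.

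**What to change.** First, reconcile the protocol passages: Table 6 and Section 7.1.3 state the QRS criterion in milliseconds, Table 14 as a percentage. This review takes no view on which is right.

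Then, before the database freeze:

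- add the reconciled QRS change-from-baseline criterion as a row in SAP 14.8.1;
- select Listing 27 on that row as well as on the absolute limits;
- report the number of participants meeting it by dose level, counting scheduled and unscheduled ECGs. This would be a new count, since SAP 14.10.5 plans no count of threshold exceedances for any ECG interval.

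The cost is one derived flag and one count on data already collected. SAP 5.3 defines the ECG baseline as the mean of the triplicate readings, and 14.6.1 defines change and percentage change, so either form of the criterion can be programmed without new definitions.

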### 14.8.2. Vital Signs

To identify heart rate values of potential clinical importance, NCI-CTCAE v5.0 will be used to assign categories that align with the grades for ‘Sinus bradycardia’, ‘Sinus tachycardia’, ‘Supraventricular tachycardia’, and ‘Ventricular tachycardia’.

The following criteria will be used to flag vital sign values that are values of potential clinical importance:

| Vital Sign Parameter | Potential Clinical Importance (PCI) Range | Unit |
|-----------------------------|--|-------------|
| Absolute Heart Rate         | <60 (Low)
>100 (High)                         | bpm         |

To identify blood pressure values of potential clinical importance, NCI-CTCAE v5.0 will be used to assign categories that align with the grades for ‘Hypertension’.

| Vital Sign Parameter       | Potential Clinical Importance (PCI) Range                   | Unit |
|-----------------------------------|--|-------------|
| Absolute Systolic Blood Pressure  | ≥120 to <140 (Grade 1)
≥140 to <160 (Grade 2)
≥160 (Grade 3) | mmHg        |
| Absolute Diastolic Blood Pressure | ≥80 to <90 (Grade 1)
≥90 to <100 (Grade 2)
≥100 (Grade 3)    | mmHg        |

To identify temperature values of potential clinical importance, NCI-CTCAE v5.0 will be used to assign categories that align with the grades for ‘Hypothermia’ and ‘Fever’.

| Vital Sign Parameter | Potential Clinical Importance (PCI) Range | Unit |
|-----------------------------|--|-------------|
| Absolute Temperature        | ≤35 (Low)
≥38 (High)                          | Degrees C   |

## 14.9. Appendix 9: Abbreviations & Trademarks

### 14.9.1. Abbreviations

| Abbreviation | Description   |
|--------------|---|
| ADaM         | Analysis Data Model   |
| AE           | Adverse Event   |
| AESI         | Adverse Event of Special Interest                                     |
| A&R          | Analysis and Reporting  |
| BOR          | Best Overall Response   |
| CDISC        | Clinical Data Interchange Standards Consortium                        |
| CI           | Confidence Interval   |
| CPMS         | Clinical Pharmacology Modelling & Simulation                          |
| CS           | Clinical Statistics   |
| CSR          | Clinical Study Report   |
| CTR          | Clinical Trial Register   |
| DBF          | Database Freeze   |
| DBR          | Database Release  |
| DEC          | Dose Escalation Committee   |
| DOB          | Date of Birth   |
| DOR          | Duration of response  |
| DP           | Decimal Places  |
| eCRF         | Electronic Case Record Form   |
| EMA          | European Medicines Agency   |
| FDA          | Food and Drug Administration  |
| FDAAA        | Food and Drug Administration Clinical Results Disclosure Requirements |
| GSK          | GlaxoSmithKline   |
| IA           | Interim Analysis  |
| ICH          | International Conference on Harmonization                             |
| IDMC         | Independent Data Monitoring Committee                                 |
| IDSL         | Integrated Data Standards Library                                     |
| IFA          | Interim futility analysis   |
| IMMS         | International Modules Management System                               |
| IP           | Investigational Product   |
| ITT          | Intent-To-Treat   |
| MTD          | Maximum-tolerated Dose  |
| N-CRM        | Neuenschwander continual reassessment method                          |
| NSCLC        | Nonsmall-cell lung carcinoma  |
| ORR          | Objective response rate   |
| OS           | Overall survival  |
| PCI          | Potential Clinical Importance   |
| PD           | Pharmacodynamic   |
| PFS          | Progression free survival   |
| PK           | Pharmacokinetic   |
| PP           | Per Protocol  |
| PopPK        | Population PK   |

| Abbreviation | Description                               |
|---------------------|--|
| QC                  | Quality Control                                  |
| QTcF                | Frederica's QT Interval Corrected for Heart Rate |
| RAP                 | Reporting & Analysis Plan                        |
| RP2D                | Recommended Phase 2 Dose                         |
| SAC                 | Statistical Analysis Complete                    |
| SAE                 | Serious Adverse Event                            |
| SDTM                | Study Data Tabulation Model                      |
| SoA                 | Schedule of Assessments                          |
| SOP                 | Standard Operation Procedure                     |
| TA                  | Therapeutic Area                                 |
| TFL                 | Tables, Figures & Listings                       |
| TTR                 | Time to response                                 |

